6.1.1.2 Participation: Proportion of eligible participants who agreed to participate

6.1.1.3 Retention: Number of participants who completed the T2 assessment divided by the number who agreed to participate

CONNECTing Caregivers to Supportive Services (CONNECT):
A Technology-Based Intervention to Connect Cancer Caregivers with Supportive Care
Resources

Wake Forest Baptist Comprehensive Cancer Center
WFBCCC # 99519

6.1.1.3.1 Acceptability: Survey developed for study to assess how much caregivers liked different aspects of CONNECT; and a ~30min (approximately) qualitative interview to further explore acceptability. (Appendices H, I, and J)

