7.3 Intervention Administration

7.3.1 Recruitment

In collaboration with the treating oncologist, patients will be identified through clinic schedules. Screened patients will be recorded in the Subject Screening Form, an excel document (Appendix M) that will be kept on a protected share drive through the Wake Forest Baptist network and is only accessible to key staff members. Patients will be recruited for the study via a mailed recruitment package (Appendix X) or message sent via myWakeHealth that notifies patients that they may be eligible to participate in the study and provides them with an option to opt out of additional contact regarding the study. Patients will then be contacted either by phone or in person (as institutional and government policies allow). At this time additional information will be provided to the patient regarding the study and their eligibility will be confirmed (see section 3.1.2.6).

For patients that are not able to communicate verbally, there is an option in the letter for them to reply to the message with the name and phone number of a caregiver with whom we can discuss the study if they are interested in learning more.

If patient is interested and has an eligible caregiver who is also interested in participating, study coordinator will proceed with consenting them (see section 6.5). If the caregiver is not present, we will seek permission from the patient to contact the caregiver by phone to discuss study participation.

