9.1 Analysis of Primary Objectives

- 9.1.1 For Objective 2.1.1, participation rate will be the percent of eligible participants who agree to participate. Accrual rate will be the number of caregivers who agreed to participate divided by the number of months of recruitment. Retention rate will be the number of participants who completed measures divided by the number who consented. We will construct 95% confidence intervals around these rates.
- 9.1.2 For Objective 2.1.2, acceptability will be summarized quantitatively and qualitatively (with assistance from WFSOM Qualitative and Patient-Reported Outcomes [Q-PRO] shared resource). Descriptive statistics (mean, standard deviation) will be used to summarize participants' acceptability rating. A codebook for analyzing qualitative interviews will be developed using a thematic analysis procedure, facilitating coding into discrete categories, and frequent themes pertinent to caregivers' likes/dislikes for CONNECT including the e-tool, message to provide re-education, and optional referral (process and navigator interaction) will be summarized. Qualitative acceptability data will be analyzed following a thematic analysis approach, facilitating coding into discrete categories.

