9.3 Power and Sample Size

The sample size is based on feasibility, and we draw on our current patient-caregiver head and neck cancer protocol (PI: [name]; IRB00038084) at the WFBCCC, prior recruitment with HNC caregivers,^{13,51,52} and clinic estimates. Our primary feasibility measures are participation, accrual, and retention rates. Assuming a negative binomial distribution and true rate of 50%, the probability that we would approach ≥ 96 dyads to recruit 40 is <0.05 . If we approach ≥ 96 dyads to enroll 40, it is unlikely the true probability is 50% or greater, and we will conclude the study may not be feasible. We anticipate accruing 40 dyads within 9 months (4-5/month). A sample size of 40 achieves 92% power to detect a difference between a mean accrual rate of 4 participants/month and an alternative mean of 3 or fewer participants/month with a significance level of 0.025 using a two-sided one-sample Poisson test. Out of the 40 participants, if the true rate of retention is 70%, we expect 23 or more will be retained (i.e., probability of $n \leq 22$ successes is <0.05); we have 85% power to test that the hypothesis that the rate is 70% compared to 50%.

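### The section 9.3 cut-off counts dyads approached, while participation is defined among the eligible, so its stated error rate holds only if nearly every approached dyad is eligible

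*Combined protocol and SAP*

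**What the plan says.** Section 6.1.1.2 defines the participation outcome as "Proportion of eligible participants who agreed to participate". Table 2 repeats this, and section 9.1.1 carries it into the analysis: "participation rate will be the percent of eligible participants who agree to participate", with a 95% confidence interval.

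Section 9.3 names participation as one of three primary feasibility measures. It then takes a true rate of 50% under a negative binomial model and states that "the probability that we would approach ≥ 96 dyads to recruit 40 is <0.05". From this it draws the inference "If we approach ≥ 96 dyads to enroll 40, it is unlikely the true probability is 50% or greater", and adds that in that case "we will conclude the study may not be feasible". The same paragraph gives accrual and retention benchmarks but attaches no conclusion to them.

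Section 7.3.1 describes the order of events. Patients are found from clinic schedules with the treating oncologist, sent a packet or portal message from which they can opt out, and then reached by phone or in person. Of that contact it says: "At this time additional information will be provided to the patient regarding the study and their eligibility will be confirmed". A caregiver who is absent may be reached later still.

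**The concern.** The rule and the outcome it judges use different denominators. The outcome divides by eligible people. The rule counts approached dyads, a term that is neither defined nor limited to the eligible. Because eligibility is settled at contact, some approached dyads may prove ineligible, for instance because there is no qualifying caregiver, no internet access, or insufficient English.

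Each such contact uses up part of the 96 without saying anything about willingness. The rule then tests willingness multiplied by screening yield, and compares the product with a benchmark meant for willingness alone. The stated error probability no longer describes participation as defined. In one dataset the rule could point to infeasibility while the reported participation rate is at or above 50%. This is the only cut-off in 9.3 with a stated conclusion, and the pilot is meant to support a larger trial.

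**Working it through.** **Inputs from section 9.3.** Target 40 dyads; cut-off 96 approached; benchmark rate 50%; negative binomial model. I take the numerator of 40 as given. Whether it means dyads recruited or dyads enrolled after T0 is a separate question.

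**Assumed input.** The share of approached dyads found ineligible, 1 − e, is not in the documents. I use 0 to 20%.

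**Step 1: the plan's own figure.** Needing 96 or more approaches to reach 40 means having at most 39 successes in the first 95:

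P(N ≥ 96) = P(Bin(95, 0.5) ≤ 39) = 0.0501.

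For 97 or more, P(Bin(96, 0.5) ≤ 39) = 0.0411. The stated figure is reproduced to rounding, but 97 is the first cut-off strictly below 0.05.

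**Step 2: allow for ineligible contacts.** If participation among eligible dyads is p and the eligible share is e, each approach succeeds with probability p × e. The rule triggers with probability P(Bin(95, p × e) ≤ 39). For example, p = 0.5 and e = 0.9 give p × e = 0.45 and a probability of 0.2521.

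| Share ineligible (assumed) | p = 50% | p = 55% | p = 60% | p = 70% |
|---|---|---|---|---|
| 0% | 0.0501 | 0.0044 | 0.0001 | <0.0001 |
| 5% | 0.1237 | 0.0186 | 0.0013 | <0.0001 |
| 10% | 0.2521 | 0.0610 | 0.0076 | <0.0001 |
| 15% | 0.4300 | 0.1562 | 0.0330 | 0.0002 |
| 20% | 0.6256 | 0.3185 | 0.1049 | 0.0024 |

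**Step 3: can rule and outcome disagree in one dataset?** With exactly 96 approached and 40 enrolled, observed participation among the eligible is 40 / (96 × e):

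- e = 1.0: 40 / 96 = 41.7%
- e = 0.9: 40 / 86.4 = 46.3%
- e = 0.8: 40 / 76.8 = 52.1%

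The ratio reaches 50% when 96 × e = 80, that is e = 80 / 96 = 0.833. Below that share the rule can trigger although observed participation is 50% or more.

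**Step 4: the same rule on eligible dyads.** With only eligible dyads counted, e drops out. At a true 50% the probability is 0.0501 with a cut-off of 96 and 0.0411 with 97, whatever the screening yield.

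**The case against.** The best reply is that this is loose wording. The rule comes directly after participation is named as a primary measure, so its 50% is naturally the rate already defined among the eligible. The rule also counts dyads, and a patient with no qualifying caregiver is arguably not a dyad. Pre-screening of schedules with the oncologist should settle stage, treatment and age before anyone is contacted. If approached was meant as eligible and approached, there is no mismatch. This is a fair reading and it lowers the likely ineligible share, but the text does not state it, and 7.3.1 leaves confirmation to the contact. At the 50% benchmark, 5% ineligible already more than doubles the error rate.

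A second reply is that contacts needed per enrolled dyad is itself useful for planning a larger trial. That is true, but it is a different quantity from participation and is clearer when reported separately.

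A reader might infer something stronger: that the rule will fail a trial whose participation is acceptable. The documents do not support that. The conclusion is worded as a possibility, no stopping action or interim analysis is attached, and participation among the eligible is reported with its confidence interval in any case. The large probabilities occur at or near 50% participation; with 10% ineligible the figure is 0.061 at 55% and 0.008 at 60%.

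A further objection stands in full. Patients can opt out before their eligibility is known, so simply saying that eligible dyads are counted leaves those people without a rule. The fix has to cover them.

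**Conclusion.** The mismatch is in the text, and it should be fixed. Read literally, section 9.3 tests a different rate from the one in 6.1.1.2 and 9.1.1, and its probability of about 0.05 applies to participation only if essentially all approached dyads are eligible. At a true 50% participation the chance of the not-feasible conclusion is 0.124, 0.252 and 0.626 with 5, 10 and 20% ineligible. At 60% participation it is 0.008 with 10% and 0.105 with 20%.

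These sizes rest on an assumed ineligible share, on treating dyads as independent with a common success probability, and on the literal meaning of approached. How large the problem is in practice cannot be known from the documents. Separately, and trivially, 96 misses the stated bound by rounding (0.0501).

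**What to change.** In section 9.3:

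1. Apply the cut-off to eligible dyads approached, meaning dyads that meet every criterion other than willingness, and say that this is the same denominator as in 9.1.1.
2. State in advance how contacts who opt out or decline before eligibility is confirmed are counted. One option is to count them as eligible in the main rule, which leans towards a not-feasible signal, and to leave them out in a sensitivity count. Use the same convention in 9.1.1.
3. Report the approached-to-eligible yield as a separate descriptive figure, so that low yield is visible and is not confused with unwillingness.
4. Set the cut-off at 97 or more, with probability 0.041 at a true 50%.

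Settle this before the counts are known, since the choice of denominator can change the conclusion. The cost is a few sentences and slightly more screening-log work to record eligibility status and the point at which each contact ended. Screened and approached people are already logged in the Subject Screening Form (Appendix M), but its fields are not shown, so an added column may be needed.

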7.3.2 Randomization Plan

Caregiver participants will be randomized to the CONNECT web-based tool (n=20) or to the generic resource list (n=20) after both the patient and caregiver in a dyad return T0 and will be considered enrolled in the study. We anticipate that some participants may drop out prior to T0, and therefore may recruit up to 50 caregiver-patient dyads to ensure 40 complete T0; this is based on a potential drop out rate of up to 20%, although it is expected be lower. Because this protocol tests a caregiver-delivered intervention, patients will not be directly randomized, though the randomization of a caregiver implies a randomization of a patient. During the enrollment process participants will be informed that they could be randomly assigned to 1 of 2 different supportive treatments (Group A or Group B) with a general description of what these groups will involve, but participants will not be blind to their treatment assignment once they begin the study. Patients will also not be blinded regarding their caregiver's assignment. Allocation to treatment arm will be computer-generated and concealed by [name] (Biostatistician). Study team members will not know group assignment when consenting participants. The Project Manager and PI who assign participants to interventions will be made aware of group assignment after both the patient and caregiver have provided informed consent and returned their baseline questionnaires.

7.3.3 Description and Procedures.

**CONNECTing Caregivers to Supportive Services (CONNECT):
A Technology-Based Intervention to Connect Cancer Caregivers with Supportive Care
Resources**

Wake Forest Baptist Comprehensive Cancer Center
WFBCCC # 99519

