9.5 Estimated Study Length

We anticipate recruitment will take approximately 9 months, with data collection complete in 12 months.

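### The 92% power stated for accrual (4 versus 3 per month) corresponds to about 40 months of observation; with about 9 months or 40 dyads it is roughly 20–48%

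*Combined protocol and SAP*

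**What the plan says.** Section 9.3 names accrual as one of three primary feasibility measures and gives it a power statement: "A sample size of 40 achieves 92% power to detect a difference between a mean accrual rate of 4 participants/month". The comparison rate is 3 per month or lower, and the test named is a one-sample Poisson test, described as two-sided, at level 0.025.

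In the same section 40 is a number of dyads or participants. The next calculation begins: "Out of the 40 participants, if the true rate of retention is 70%, we expect 23 or more will be retained".

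Section 9.1.1 defines the measure: "Accrual rate will be the number of caregivers who agreed to participate divided by the number of months of recruitment". The analysis planned for it is an interval: "We will construct 95% confidence intervals around these rates".

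Section 9.5 gives the recruitment period: "We anticipate recruitment will take approximately 9 months, with data collection complete in 12 months". Section 7.3.2 allows for loss before baseline: the study "may recruit up to 50 caregiver-patient dyads to ensure 40 complete T0".

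**The concern.** A one-sample Poisson test of a monthly rate compares a count with the rate multiplied by the months observed. Forty dyads recruited over about 9 months supply about 9 months of exposure and about 40 events. They are not 40 separate observations that each have a mean of 4 or 3 per month. A figure of 92% looks far too high for separating 36 expected events from 27.

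What is at stake is how the accrual result is read. The pilot is meant to support a larger pragmatic trial. A reader who trusts 92% could treat a rate of 3 per month as ruled out when data of this size often cannot rule it out.

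**Working it through.** **Inputs.** Null rate 4 per month, alternative 3 per month, alpha 0.025, described as two-sided, one-sample Poisson (9.3). Recruitment about 9 months (9.3, 9.4, 9.5). 40 dyads (9.3), or up to 50 consenting (7.3.2). I also use 10 months, because 40 dyads at exactly 4 per month take 40/4 = 10 months.

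The plan does not say how alpha is split, so each result is given two ways: 0.025 in the lower tail, and 0.0125 per tail (the literal two-sided 0.025). Power is evaluated at 3 per month, the boundary of the stated alternative.

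**Formulas.**
- Fixed window of m months, exact: the count is Poisson(rate × m). Reject if the count is at most c, where c is the largest value with P(count ≤ c | 4m) no greater than the lower-tail alpha. Power is P(count ≤ c | 3m).
- Fixed window, normal with the alternative variance: power = Φ[(4m − 3m)/√(3m) − z] = Φ[√(m/3) − z].
- Recruitment stopped at the nth dyad: elapsed time is Gamma(n, rate). Reject if the time exceeds the upper-alpha quantile at rate 4. Power is the probability of exceeding it at rate 3.

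**Reproducing 92%.** Put m = 40 months, so the expected counts are 160 and 120.
- Exact, 0.025 in the lower tail: reject at ≤ 135, size 0.0241, power 0.9194.
- Normal, alternative variance, z = 2.2414 (two-sided 0.025): Φ(√(40/3) − 2.2414) = Φ(1.410) = 0.9207.
- Exact, 0.0125 per tail: reject at ≤ 131, power 0.853. Under this literal reading 92% would need about 48 months.

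So the stated figure appears when 40 is read as months. No passage plans 40 months or 120–160 participants.

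**What the planned design gives at 3 per month.**

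| Design | 0.025 lower tail | 0.0125 per tail |
|---|---|---|
| 9 months, exact (36 vs 27) | reject ≤ 24: 32.4% | reject ≤ 22: 19.5% |
| 10 months, exact (40 vs 30) | reject ≤ 27: 33.3% | reject ≤ 26: 26.7% |
| Stop at 40th dyad | time > 13.33 months: 48.0% | time > 13.87 months: 38.0% |
| Stop at 50th dyad | time > 16.20 months: 56.1% | time > 16.79 months: 46.0% |

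The normal formula at two-sided 0.025 gives Φ(√3 − 2.2414) = 30.5% at 9 months and Φ(√(10/3) − 2.2414) = 33.9% at 10 months. With 0.025 in the lower tail (z = 1.960) it gives 41.0% and 44.7%.

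Sustained exact power of at least 80% would need about 30 months (0.025 lower tail) or 36 months (0.0125 per tail).

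**What the planned interval would show.** The exact Poisson 95% limits for a count of 40 are 28.58 and 54.47. Divided by months:
- 40 in 9 months (4.4 per month): 3.18 to 6.05, excludes 3.
- 40 in 10 months (4.0 per month): 2.86 to 5.45, contains 3.
- 40 in 13.33 months (3.0 per month): 2.14 to 4.09, contains 4.

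**The case against.** The strongest reply is that nothing depends on this figure. Section 9.3 opens by saying the sample size rests on feasibility, it attaches no go/no-go conclusion to accrual, and 9.1.1 plans an interval and no Poisson test. This stands, and it limits the consequence: the error sits in a supporting statement. It does not make the statement right, and the statement concerns a primary measure.

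Second, if recruitment goes as anticipated, with 40 dyads in 9 months, the interval of 3.18 to 6.05 does exclude 3. That is true and should be said. It describes an observed rate of 4.4 per month, above the null of 4. At exactly 4 per month the interval contains 3. The overlap at 3 per month is narrow (upper limit 4.09), because 13.33 months is almost exactly the one-tail rejection cutoff.

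Third, the alternative is 3 or fewer. Larger shortfalls are easier to detect: exact power at 2 per month is 86–93% over 9 months and 92–95% over 10. The 20–48% therefore applies at 3 per month. Since 3 is the stated boundary, a claim covering 3 or fewer must hold there.

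Finally, the plan shows neither formula nor software, so entering 40 as months is an inference from the match. The conclusion does not need it: no reading with 9 or 10 months, 40 dyads or 50 dyads comes near 92%.

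**Conclusion.** The concern holds. The stated 92% fits about 40 months of observation. At a true rate of 3 per month, the planned 9–10 months or 40 dyads give about 20–48%, depending on the test formula, the per-tail alpha, and whether the window or the count is fixed. Counting all 50 dyads raises this only to 46–56%. These figures assume Poisson accrual at a constant rate. Taking the two-sided 0.025 literally with an exact test makes the stated figure harder to support: 85.3% even at 40 months.

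The error overstates how well accrual can be judged in this pilot. It leaves the accrual estimate, its confidence interval and the feasibility-based sample size unaffected. It should be corrected.

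**What to change.** Change 9.3 in one of two ways.

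1. Replace 92% with the power the design delivers at 3 per month, and state the formula, the alpha in each tail, and whether the recruitment window or the number of dyads is fixed.
2. Drop the power claim and give the expected precision of the interval planned in 9.1.1: about 3.2 to 6.1 per month for 40 dyads in 9 months, or 2.9 to 5.4 per month for 40 in 10 months.

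The second is simpler and matches the planned analysis, since no Poisson test is planned. Either takes one or two sentences and replaces a favourable figure with a less favourable one. The sample size should stay as it is, and no participants, procedures or analyses are added.

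### The 85% retention power does not belong to the printed cut-off of 22 or fewer of 40, whose exact power against a true rate of 50% is 78.5%

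*Combined protocol and SAP*

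**What the plan says.** Section 9.3 (Power and Sample Size) names participation, accrual and retention as the primary feasibility measures. Its retention sentence has two parts.

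- A cut-off: "Out of the 40 participants, if the true rate of retention is 70%, we expect 23 or more will be retained", because the probability of 22 or fewer is put below 0.05.
- A power statement, after a semicolon: "we have 85% power to test that the hypothesis that the rate is 70% compared to 50" per cent.

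Neither part names a test, a significance level or sidedness for the power. The accrual sentence just before gives all three: "with a significance level of 0.025 using a two-sided one-sample Poisson test".

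For the analysis, Section 9.1 (Analysis of Primary Objectives) plans estimation of the participation, accrual and retention rates: "We will construct 95% confidence intervals around these rates". It names no test of retention.

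**The concern.** A reader will attach the 85% to the cut-off printed immediately before it, since that is the only retention cut-off in the plan. With only 40 binary outcomes, moving the cut-off by one participant changes power by about 8 points, so a power figure is informative only if it belongs to the cut-off beside it.

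If it does not, the plan overstates how well this check would detect that retention is really 50%. Retention is one of three primary measures in a pilot meant to support a larger trial, so the stated sensitivity should be the one the rule delivers.

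**Working it through.** **Inputs, all from Section 9.3:** n = 40; reference retention rate 0.70; alternative 0.50; cut-off 22 or fewer retained; tail probability at 70% below 0.05; stated power 85%.

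**Step 1. Reproduce the cut-off.** The exact binomial probability is P(X ≤ k) = Σ C(40, x) pˣ (1 − p)⁴⁰⁻ˣ, summed over x = 0 to k.

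| Cut-off k | P(X ≤ k) at 70% (type I error) | P(X ≤ k) at 50% (power) |
|---|---|---|
| 21 | 0.0148 | 0.6821 |
| 22 | 0.0320 | 0.7852 |
| 23 | 0.0633 | 0.8659 |

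The cut-off is correct: 22 is the largest count with probability below 0.05 at 70%.

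**Step 2. Reproduce the 85%.** Take a one-sample normal approximation, one-sided 0.05, with the null standard error and no continuity correction.

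- Null standard error: √(0.7 × 0.3 / 40) = 0.0725.
- Critical proportion: 0.7 − 1.645 × 0.0725 = 0.5808, which is 0.5808 × 40 = 23.2 participants.
- Standard error at 50%: √(0.5 × 0.5 / 40) = 0.0791.
- Power: Φ((0.5808 − 0.5) / 0.0791) = Φ(1.02) = 0.847.

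This rounds to 85%. Other versions do not:

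- with continuity correction: 80.6%;
- two-sided 0.05, uncorrected: 76.8% (critical count 22.3);
- hypotheses reversed (50% as the null), one-sided 0.05: 83.3% by normal approximation, and 80.7% by exact binomial (reject at 26 or more, error 0.0403).

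**Step 3. Compare the two rules at 23 retained.**

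- The approximate test gives z = (0.575 − 0.7) / 0.0725 = −1.725, one-sided p = 0.042, so it rejects 70%. The exact error of a rule that rejects at 23 or fewer is 0.063.
- The plan's sentence counts 23 among the results to be expected at 70%: "we expect 23 or more will be retained".

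At 22 retained the two agree (z = −2.070, p = 0.019). They part at exactly 23.

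**Step 4. Power of the printed cut-off.** From the table, P(X ≤ 22) at 50% is 0.7852, or 78.5%. The difference from the stated figure is 85 − 78.5 = 6.5 points. The chance of missing a true 50% rate is 1 − 0.785 = 21.5%, against the 15% implied. One cut-off higher, power is 86.6% but the tail probability at 70% is 0.0633, which breaks the plan's own condition.

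**The case against.** The strongest reply is that 85% is not a miscalculation. A standard large-sample formula gives 84.7%, and the text never says that 22 or fewer is a rejection region. The cut-off can be read as an illustration of what to expect at 70%, with the power as a separate statement about an unnamed test. A rule of 23 or fewer is also defensible at one-sided 0.05 by the z-test, and by mid-p: 0.0320 + ½ × (0.0633 − 0.0320) = 0.048. On that reading the sentence lacks a label, and preferring the exact tail is partly a matter of choice.

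Much of this stands. The formula is legitimate, its use here is inferred from the match, and the plan does not define a rejection region. But the exact tail is the plan's own choice, since it is what its below-0.05 statement about 22 or fewer matches. If the 85% belongs to another test, that test rejects at a count which the same sentence treats as compatible with 70%, and the reader is not told. Either way the two halves of the sentence do not describe one rule.

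It is also fair to say that little depends on the figure. Section 9.3 says the sample size rests on feasibility and attaches a feasibility conclusion only to participation. The confidence interval planned in Section 9.1 does not use the 85%.

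**Conclusion.** The concern holds. The cut-off is right and the 85% follows from a recognised approximation, but the printed cut-off does not deliver that power. Its exact power against 50% is 78.5% at an exact one-sided error of 0.032, so the stated figure is about 6.5 points too favourable.

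This rests on three assumptions: that 22 or fewer is the rule the power should describe, being the only retention cut-off given; that the denominator is 40, as in Section 9.3; and that participants are retained or lost independently with a common probability. The binomial figures are certain under these assumptions; the source of the 85% is an inference.

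The point is worth correcting because the figure is wrong as paired, but it does not threaten the design, the planned estimates or any stated decision.

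**What to change.** In the retention sentence of Section 9.3, replace the 85% with about 79% and add a short method label: exact binomial, one-sided, 22 or fewer of 40, type I error 0.032. The cut-off and the expectation of 23 or more can stay.

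If the sponsor did mean the approximate test, keeping 85% would require naming that test, its level and sidedness, and saying that it rejects at 23 or fewer with exact error 0.063. The sentence could then no longer treat 23 as compatible with 70%. Restating the power is the simpler change.

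The cost is one figure and a few words. Sample size, estimates, confidence intervals and stated decisions are unaffected; the quoted power becomes slightly less favourable.
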